1.2 OBJECTIVES

1.2.1 Primary objectives

To evaluate the efficacy of sarilumab in patients with GCA as assessed by the proportion of patients with sustained remission at Week 52 for sarilumab compared to placebo, in combination with a 26-week CS tapering course.

1.2.2 Secondary objectives

- To demonstrate the efficacy of sarilumab in patients with GCA compared to placebo, in combination with (either 26 or 52 weeks) CS tapering course with regard to:
 - Clinical responses (such as responses based on disease remission rates, time to first disease flare) over time.
 - Cumulative CS (including prednisone) exposure.
- To assess the safety (including immunogenicity) and tolerability of sarilumab in patients with GCA.
- To measure sarilumab serum concentrations in patients with GCA.
- To assess the effect of sarilumab on sparing glucocorticoid toxicity as measured by glucocorticoid toxicity index (GTI).

1.2.3 Other objectives

- To assess the effect of sarilumab on physician assessment of disease activity as measured by a visual analogue scale (MD-VAS).
- To assess the effect of sarilumab compared with placebo, in combination with a 26-week CS taper as on a variety of patient reported outcome (PRO) concepts including fatigue (FACIT-Fatigue), health status (EuroQol five-dimensional three-level questionnaire [EQ-5D-3L], Short form 36 version 2 [SF-36v2]), physical functioning (health assessment questionnaire disability index [HAQ-DI]), including pain (visual analogue scale) and patient assessment of disease activity (visual analogue scale).
- To assess the impact of ESR/CRP levels on remission status.

- To characterize the disease activity of GCA patients while on steroid taper or sarilumab treatment in a subset of patients using comprehensive approaches to evaluate circulating immune cell types.
- To characterize the disease activity of GCA patients while on steroid taper or sarilumab treatment by evaluating circulating proteins, genetics and gene expression in consenting patients.

1.3 DETERMINATION OF SAMPLE SIZE

The sample size calculations are based on the primary efficacy variable of sustained remission at Week 52. Data from another trial that evaluated the safety and efficacy of tocilizumab in a similar population show that the expected event rate in Group C (placebo with 26-week taper, n = 60) is 14% and in Group D (placebo with 52-week taper, n = 120) is 18% (1). Assuming a treatment difference of 40% and a significance level of 0.01 (2-sided) this will ensure that all comparisons of the primary endpoint in Group A (sarilumab 200 mg, n = 120) and Group B (sarilumab 150 mg, n = 60) compared to the 2 control groups will have at least 90% power. The sample size has also been selected to ensure adequate power for sensitivity analyses excluding acute phase reactants from the primary endpoint definition.

The above calculations were for the full enrollment. However, the number of randomized patients is 83 in 4 arms at the time of the premature termination of the study. In addition, based on patients' enrollment dates and the study discontinuation plan, only about 36 patients (out of 83) had an opportunity to complete the 52-week treatment period. For the cohort of patients who did not have an opportunity to complete the 52-week treatment period, it is not meaningful to define the endpoint of sustained remission at Week 52. Therefore, the analysis of primary endpoint will be limited to the cohort of patients who had an opportunity to complete the 52-week treatment period. Due to the small number of patients (n=36) in this cohort (see Section 2.3.1 for definition of the cohort), the powers on the primary endpoint are minimal. As a result, all the efficacy analyses will be descriptive in nature and all reported p-values will be nominal for the study.

Based on patients' enrollment dates, all enrolled patients (n=83) had an opportunity to complete at least 24 weeks of treatment, therefore, an additional endpoint, sustained remission at Week 24 is added in the SAP (see Section 2.1.3.1 for the detail definition). Table 1 provides the power calculations on the additional endpoint of sustained remission at Week 24. Due to the small number of patients in each individual treatment group, the power calculations were also provided for the comparison between the combined sarilumab groups (i.e., Group A+B) and the combined placebo groups (i.e., Group C+D) assuming the same effect sizes as mentioned above.

Table 1: Updated power calculations

Treatment	Estimate of the sustained remission rate	Estimated Sample size	Comparison	Power [1] (%)	Power [2] (%)
Group A	54%	28	Group A versus Group C	45.7	74.0
Group B	50%	14	Group A versus Group D	58.6	81.1

Group C	14%	14
Group D	18%	27
Group A + B (combined sarilumab)	53%	42
Group C + D (combined placebo)	17%	41

Group B versus Group C	28.1	53.5
Group B versus Group D	33.6	57.1
Group A+B versus Group C+D	82.3	94.5
Power [1] was based on an alpha level of 0.01. Power [2] was based on an alpha level of 0.05.		

Treatment Group A: sarilumab 200 mg q2w with a 26 week taper of CS.

Treatment Group B: sarilumab 150 mg q2w with a 26 week taper of CS.

Treatment Group C: sarilumab matching placebo q2w with a 26 week taper of CS.

[figure not shown]
Treatment Group D: sarilumab matching placebo q2w with a 52 week taper of CS.

Powers were calculated using the Chi-square test for each comparison; Calculations were made using nQuery Advisor 7.0.

1.4 STUDY PLAN

The schedule of the safety, efficacy, pharmacokinetic (PK), and immunogenicity assessments from Section 1.2 of the study protocol is provided in [Appendix A](#). The graphical study design is provided in [Figure 1](#).

Figure 1 – Graphic study design

Patients will be randomized to 4 groups with the ratio of 2:1:1:2

*Patients experiencing a disease flare may be rescued with open-label treatment as per Investigator judgment during the study treatment period.

1.5 MODIFICATIONS TO THE STATISTICAL SECTION OF THE PROTOCOL

There was one protocol amendment for EFC15068 study (see [Table 2](#)). The overall rationale for the changes implemented in the protocol amendment 01 was to address several comments raised by the European Regulatory Authorities during the initial protocol review. The changes made in the statistical section in the protocol amendment 01 are summarized in [Table 3](#).

Table 2: Protocol amendment history

Document	Country/Countries impacted by amendment	Date, version
Amended Clinical Trial Protocol 01	All	12-Sep-2018, version 1 (electronic 2.0)
Original Protocol	All	09-Feb-2018, version 1 (electronic 4.0)

Table 3: Summary of changes of the statistical section - Protocol amendment 01

Section # and Name	Description of Change	Brief Rationale
Clinical Trial Summary –Statistical Consideration AND Section 11.1 Determination of sample size	More details on the power calculations were added.	The assumed treatment effects used for the power calculations were added for clarity.
Section 11.4.2.1 Analysis of primary efficacy endpoint(s)	The non-inferiority test between Sarilumab 200 mg q2w arm and the placebo with 52 weeks taper arm was removed.	Based on the results from the GiACTA study, the non-inferiority test is deemed as unnecessary and thus removed from the protocol
Section 11.4.2.3 Multiplicity considerations	The hierarchical testing approach including the testing sequence for the secondary endpoints were clarified.	Details on the hierarchical testing sequence for the secondary endpoints were added for clarification to address a specific request from the European Regulatory Authorities.

1.6 STATISTICAL MODIFICATIONS MADE IN THE STATISTICAL ANALYSIS PLAN

Due to the early termination of the study and study discontinuation plan, a large amount of data will not be able to be collected since many enrolled patients will not complete all planned study visits and study procedures for the assessments of efficacy, ADA, and biomarker endpoints. In addition, the number of randomized patients is 83 in 4 arms (out of 360 planned) at the time of the premature termination of the study. The changes from the statistical analysis plan outlined in the protocol are summarized below.

- The primary endpoint for the study is sustained remission at Week 52. Based on patients' enrollment dates and the study discontinuation plan, only about 36 patients (out of 83) had an opportunity to complete the 52-week treatment period. For the cohort of patients who

did not have an opportunity to complete the 52-week treatment period, it is not meaningful to define the endpoint of sustained remission at Week 52. Therefore, the analysis of primary endpoint will be limited to the cohort of patients who had an opportunity to complete the 52-week treatment period. Details can be found in [Section 2.1.3.1](#) and [Section 2.4.4.1](#).

- Based on patients' enrollment dates and the study discontinuation plan, all patients should have had the opportunity to be treated for at least 24 weeks, so an additional endpoint, sustained remission at Week 24, is added in the SAP. Details can be found in [Section 2.1.3.1](#).
- Due to the same reason as mentioned above, the secondary endpoints of cumulative GTI scores at Week 52 will be limited to the cohort of patients who had an opportunity to complete the 52-week treatment period. In addition, the cumulative GTI scores will also be assessed at Week 24. Details are provided in [Section 2.1.3.2](#).
- The missing data imputation strategy for defining the endpoints of sustained remission at W24 and W52, and cumulative GTI scores at W24 and W52 can be found in [Section 2.1.3.1](#) and [Section 2.1.3.2](#), respectively; the rest of efficacy analyses will be based on data as observed, no missing data will be imputed.
- A statistically significance level of 0.01 (2-sided) was prespecified in the protocol for all the between group comparisons. Due to reason mentioned in the first bullet, the analysis of the primary endpoint of sustained remission at Week 52 will be limited to the cohort of patients who had an opportunity to complete the 52-week treatment period (n=36). With a total of 36 patients, the powers on the primary endpoint are minimal. Therefore, all the analyses will be descriptive in nature.
 - a) For majority of the efficacy endpoints, only descriptive summary statistics will be provided by 4 treatment groups.
 - b) For the primary and some selected important secondary endpoints, summary statistics and formal statistical tests on between group comparisons (with 95% CI and p-value) will be provided for the 2 combined treatment groups (ie, 2 sarilumab groups combined versus 2 placebo groups combined). Details are provided in [Section 2.4.4](#).
- No multiplicity/hierarchy testing will be applied; all p-values will be nominal.
- No subgroup analyses will be planned due to the small sample sizes.

2 STATISTICAL AND ANALYTICAL PROCEDURES

Data analyses will be performed in the double-blind (DB) 52-week treatment period. The analysis results will be presented by 4 treatment groups (Groups A, B, C and D) in the DB assessment period. The posttreatment follow-up phase will be presented separately without formal statistical testing as needed.

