4.1 BENEFIT AND RISK ASSESSMENT

The available aggregate nonclinical and clinical data from the sarilumab development program in RA have demonstrated a potent anti-inflammatory effect and significant clinical benefit for patients with active RA via blockade of the IL-6 signaling pathway, which is also thought to play a key role in the pathogenesis of GCA. Therefore, treatment of GCA patients with sarilumab may lead to clinical benefits as observed in patients with active RA. This likely benefit with sarilumab is further supported by the pivotal GiACTA trial (a phase 3 study which evaluated efficacy and safety of tocilizumab in GCA patients [9]) that resulted in the approval of a similar IL-6 inhibitor, tocilizumab, for the treatment of GCA. Because of the similarity of sarilumab to tocilizumab and a study design that mirrors the successful GiACTA trial, it is expected that the current study will demonstrate a similar efficacy for sarilumab in GCA. Sarilumab is already approved for the treatment of rheumatoid arthritis in multiple countries.

Based on the safety profile of sarilumab available to date and other biological DMARDs, important identified risks include serious infections, neutropenia and hypersensitivity reactions; important potential risks to be considered with sarilumab administration, consistent with this class of therapy, include laboratory abnormalities and the potential clinical consequences, such as thrombocytopenia and the potential risk of bleeding, clinically evident hepatic injury with elevated hepatic transaminases, and lipid abnormalities and potential increased risk of major adverse cardiovascular event (MACE). Other potential important risks include increased risk of malignancy and gastrointestinal perforation. Various risk mitigation strategies are either built into the eligibility criteria (Section 7.1 and Section 7.2) to exclude those with conditions that may jeopardize their safety or into other sections of the protocol (Section 10.4 and Section 10.7) for monitoring and management of certain risks/adverse events (eg, neutropenia, thrombocytopenia, liver transaminase elevation, etc).

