1 OVERVIEW AND INVESTIGATIONAL PLAN

This statistical analysis plan (SAP) provides a comprehensive and detailed description of statistical strategy and methodology to be used to analyze the data from sarilumab EFC15068 study in patients with giant cell arteritis (GCA).

Due to the ongoing pandemic of COVID-19 (the disease caused by the novel coronavirus), the operations of sarilumab (Kevzara®) clinical trial EFC15068 have been significantly disrupted in various countries and sites. Consequently, the screening/recruitment activities for this study have been suspended since 19th of March 2020. Due to the protracted recruitment timeline and internal portfolio reprioritization, in July 2020, Sanofi has decided not to re-open the screening/recruitment activities and to discontinue the study. This decision is not related to any safety issues arising from the administration of sarilumab.

A total of 83 patients (out of 360 planned patients) have been randomized in the study. While the number of randomized patients may not be adequate to demonstrate a statistically significant benefit, the data generated from the treated patients may contribute to the further understanding of IL-6 signaling blockade in this disease state.

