2.4.5 Analyses of safety data

The summary of safety results will be presented by treatment groups.

General common rules

All safety analyses will be performed on the safety population as defined in [Section 2.3.2](#), unless otherwise specified, using the following common rules:

- Safety data in patients who do not belong to the safety population (eg, exposed but not randomized) will be listed separately
- The baseline value is defined as the last available value prior to the first dose of study medication.
- The potentially clinically significant abnormality (PCSA) values are defined as abnormal values considered medically important by the Sponsor according to predefined criteria/thresholds based on literature review and defined by the Sponsor for clinical laboratory tests, vital signs, and ECG (PCSA in BTD-009536 version 3, see [Appendix B](#))
- PCSA criteria will determine which patients had at least 1 PCSA during the TEAE period, taking into account all evaluations performed during the TEAE period, including nonscheduled or repeated evaluations. The number of all such patients will be the numerator for the on-treatment PCSA percentage
- The treatment-emergent PCSA denominator by group for a given parameter will be based on the number of patients assessed for that given parameter in the treatment-emergent adverse event period by treatment group on the safety population.
- For quantitative safety parameters based on central laboratory/reading measurements, descriptive statistics will be used to summarize results and change from baseline values by visit and treatment group. Summaries will include the endpoint value. The endpoint value is commonly defined as the value collected at the same day/time of the last dose of investigational product. If this value is missing, this endpoint value will be the closest one prior to the last dose intake.
- Analyses of the safety variables will be essentially descriptive and no systematic testing is planned.

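### Safety is planned only in four small groups; combined sarilumab and placebo columns, with the taper mixing disclosed, would be a cheap improvement

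*SAP*

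**What the plan says.** SAP 1 reports that "A total of 83 patients (out of 360 planned patients) have been randomized in the study". SAP 1.6 and 2.4.4 respond to the small groups for efficacy. The primary and some secondary endpoints receive an added analysis, in which "summary statistics and formal statistical tests on between group comparisons (with 95% CI and p-value) will be provided for the 2 combined treatment groups". No formal comparisons are made among the four individual groups. SAP 2.4.4.1 treats the added Week 24 endpoint the same way. Most other efficacy endpoints are summarised by the four groups only.

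For safety, the general rule in SAP 2 is "The analysis results will be presented by 4 treatment groups (Groups A, B, C and D) in the DB assessment period", and SAP 2.4.5 says "The summary of safety results will be presented by treatment groups". Adverse-event percentages use the safety population in each group (SAP 2.4.5.1). Laboratory summaries and Kaplan-Meier times to onset are by treatment group (SAP 2.4.5.3). No combined safety column appears in SAP 2.4.5 or in the Appendix C summary. Safety is descriptive, with no systematic testing.

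Protocol 4.1 says that "important identified risks include serious infections, neutropenia and hypersensitivity reactions". Safety and tolerability of sarilumab in GCA is a secondary objective in both documents.

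**The concern.** The small groups that led the SAP to pool key efficacy endpoints are the same groups in which safety is displayed. The secondary objective concerns sarilumab as such, not one dose. Any randomized patient who received a dose contributes to safety, whereas the Week 52 analysis is limited to 36 patients.

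Under the planned layout, a reader interested in neutropenia or serious infection on sarilumab sees one column of about 28 and another of about 14, with no interval. For onset of Grade 3 or 4 neutropenia or of ALT elevation, the reader sees separate curves on those small numbers and no sarilumab curve. What is at stake is how clearly a truncated trial reports risks that its own protocol names.

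**Working it through.** **Inputs.** SAP Table 1 gives estimated group sizes A 28, B 14, C 14 and D 27, with totals "Group A + B (combined sarilumab) 53% 42" and "Group C + D (combined placebo) 17% 41". They sum to 83. These are estimated randomized numbers; the documents give no safety-population counts. They give no expected adverse-event rates either, so the rates below are assumptions.

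**The SAP's own power figures.** Table 1 states: "Power [1] was based on an alpha level of 0.01. Power [2] was based on an alpha level of 0.05". With the pooled-variance chi-square formula, 2-sided at 0.01, power = Φ[(|p1 − p2| − 2.576·se0)/se1].
- A v C: pooled rate (28×0.54 + 14×0.14)/42 = 0.407; se0 = 0.1608; se1 = 0.1322. Power = Φ(−0.107) = 45.7%, as stated.
- A+B v C+D: pooled rate (42×0.53 + 41×0.17)/83 = 0.352; se0 = 0.1049; se1 = 0.0968. Power = Φ(0.928) = 82.3%, as stated.

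All ten powers in the table reproduce within 0.1 point, so the group sizes are a sound basis for what follows.

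**What can be rebuilt from the planned tables.**
- Patient counts add, because the groups do not overlap.
- Means and SDs follow from the planned n, mean and SD: total sum of squares = Σ(n−1)s² + Σn(group mean − grand mean)².
- A pooled median is not a function of the group medians.
- A pooled Kaplan-Meier curve needs events and numbers at risk at every event time. The SAP does not commit to tabulating these.
- No interval for a sarilumab-placebo difference is planned for any safety outcome.

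**Precision in one column.** With zero events, the exact 2-sided 95% upper bound is 1 − 0.025^(1/n):
- n = 14: 23.2%
- n = 28: 12.3%
- n = 42: 8.4%

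**Precision of a contrast.** Half-width = 1.96·√[p1(1−p1)/n1 + p2(1−p2)/n2]. For 10% v 5%:
- A v C: 1.96·√(0.09/28 + 0.0475/14) = 15.9 points
- A+B v C: 1.96·√(0.09/42 + 0.0475/14) = 14.6 points
- A+B v C+D: 1.96·√(0.09/42 + 0.0475/41) = 11.3 points

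The same formula under other assumed rates:

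| Assumed rates | A v C | A+B v C | A+B v C+D |
|---|---|---|---|
| 10% v 2% | 13.3 | 11.7 | 10.0 |
| 10% v 5% | 15.9 | 14.6 | 11.3 |
| 20% v 5% | 18.7 | 16.6 | 13.8 |

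The half-widths show scale only. Group C would expect 0.05×14 = 0.7 events, too few for this approximation to be used in reporting.

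**Steroid exposure in the pooled placebo group.** Protocol Appendix B, 60 mg start: the weekly daily doses sum to 376 mg in the 26-week regimen and 556 mg in the 52-week regimen. Multiplied by 7 days, per-protocol prednisone is 2,632 mg and 3,892 mg, a difference of 1,260 mg (48%). All of A+B follow the shorter taper, while 27 of 41 in C+D (66%) follow the longer one.

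**The case against.** The strongest objection is that A+B versus C+D is not a clean drug contrast. Placebo patients mostly have more steroid, and the protocol counts infection among glucocorticoid toxicities (9.2.1.4) and says that corticosteroid use raises the risk of gastrointestinal perforation (10.7.6). A sarilumab effect on infection could be masked. Protocol 6.5 makes A versus C primary because the tapers match. Pooling doses also hides any dose relation. All of this stands. It limits what the pooled contrast can mean and requires the four columns to stay. It does not argue against a combined sarilumab column, in which both groups share the 26-week taper.

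Three stronger readings are tempting, and the documents do not support them.
- A reader might infer that the SAP is inconsistent in pooling for efficacy but not safety. Pooling is confined to selected endpoints with formal tests. Safety has no tests and is handled like most efficacy endpoints, so no commitment is broken.
- A reader might infer that events would be missed, or that pooled SDs are lost. Every event is tabulated whichever column it falls in, and SDs can be rebuilt.
- A reader might infer that A+B versus C+D is the best safety comparison available. It is the narrowest, but most of the narrowing beyond A v C comes from adding Group D: 15.9 to 14.6 points from adding B, then 14.6 to 11.3 from adding D.

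**Conclusion.** The point holds as a modest improvement in presentation. The planned summaries provide no pooled onset curves, no pooled medians and no sarilumab-versus-placebo interval for the identified risks, although the data could support them.

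A combined sarilumab column lowers the zero-event upper bound from 23.2% (Group B) or 12.3% (Group A) to 8.4%. At 10% v 5%, the contrast half-width falls from 15.9 points (A v C) to 14.6 with the taper matched, or 11.3 with tapers mixed.

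These figures rest on the estimated group sizes in SAP Table 1 and on assumed event rates. They illustrate precision; they do not measure lost information on patient counts, which remain recoverable.

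**What to change.** In SAP 2 and 2.4.5:
- Keep the four columns. Add combined A+B and C+D columns to the TEAE, SAE, discontinuation, AESI, PCSA, laboratory and time-to-onset outputs.
- Give risk differences with 95% CIs, labelled descriptive, for serious infection and neutropenia. Use an exact or score method because counts will be sparse.
- Do the same for hypersensitivity once a search definition is written. Protocol 11.4.3.1 lists systemic allergic reactions as an AESI category with coding to follow in the SAP, but SAP Table 5 has no such category.
- State that C+D mixes 26- and 52-week tapers and that A+B mixes doses. For steroid-related events such as infection, show A+B versus C beside A+B versus C+D.
- Use actual safety-population denominators, and settle the layout before treatment codes are opened so that it is not chosen after seeing results.

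The cost is extra columns, one search definition and a short paragraph of SAP text. No new data are needed and no planned output is removed.
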